## “Angiomatoid Fibrous Histiocytoma: a single institution case-series”

Study code	AFH
Sponsor's Name and Address:	Istituto Ortopedico Rizzoli [name]
Study Number/Version/Date:	Vers 1.0 03 Sep 2018
Coordinating Center:	IRCCS Istituto Ortopedico Rizzoli Pathology Unit [name]
Coordinating Investigator and address:	[name] MD [contact] Email: [contact]
Methodology:	Experimental study with biological material (Single institution case series review of clinical and histological data)
Type:	Academic
Founding:	None
Principal Investigator Signature	I confirm that I've read this protocol and I accept to run the study in compliance with what is stated in the protocol and with the ICh-GCP and all applicable law  [name] MD  Firma  <hr/>

**BACKGROUND**

One of the many diagnostic challenges in soft tissue pathology is the AFH – the Angiomatoid Fibrous Histiocytoma. It is a rare tumor of intermediate biological potential and uncertain differentiation accounting for approximately of 0,3% of all soft tissue tumors (Thway & Fisher, 2015). The AFH is a histiocytoid cell lesion with primary histological characteristics which include in the first place a lymphocytic cuff, a fibrous pseudocapsule and pseudoangiomatoid spaces with hemorrhage and hemosiderin deposition. Unusual but often present morphological features are also a sclerotic matrix, a myxoid stroma, the presence of osteoclasts and/or a reticulated pattern. Nuclear atypia, mitosis and eosinophils can also be found (Bohman, Goldblum, Rubin, Tanas, & Billings, 2014; Kao et al., 2014)

Its name still stems from when it was first described by Enzinger in 1979 as an 'Angiomatoid malignant fibrous histiocytoma' to acknowledge for its potential for metastasis and local recurrence and it was first classified as a malignant tumor although later on its proven actual relatively low risk for distant metastasis (<5%) was considered and the word 'malignant' was removed from its name, hence 'AFH' (Bohman et al., 2014; Thway & Fisher, 2015). Clinically, its true potential for local recurrence is being estimated to be as high as 15% (Thway & Fisher, 2015). Although the tumor cells stain in a higher percentage for Desmin (50-92%), EMA (50-60%), CD68 (33-80%) and CD99 (up to a 100%), those markers are very little specific and molecular techniques such as FISH and PCR are recommended to make the diagnosis of an AFH with either one of the three translocations EWSR1-CREB1 (72%); EWSR1-ATF1 (21%) and FUS-ATF1 (7 %) being almost pathognomonic even though other tumors such as Clear cell sarcoma, Primary pulmonary myxoid sarcoma or the Hyalinizing clear cell carcinoma of the salivary gland harbor these mutations as well (Antonescu et al., 2007; Bohman et al., 2014; Chen et al., 2011; Kao et al., 2014; Rossi et al., 2007; Tanas et al., 2010; Thway & Fisher, 2015). There is a certain number of AFH which are negative for all rearrangement with FISH and it is being suggested that cryptic rearrangements of these genes undetectable by FISH or the existence of other translocations involving other genes account for these cases (Tanas et al., 2010; Thway & Fisher, 2015). Most likely FISH doesn't allow for detection of rearrangement due to the presence of submicroscopic insertions or because the genetic material simply is undetectable to the commercial break-apart probes (Thway & Fisher, 2015). RT-PCR is recommended to be performed in conjunction with FISH and even though FISH with break apart probes is faster and according to some more sensitive RT-PCR is far more specific as it also

identifies the fusion partner (Noujaim et al., 2017; Thway & Fisher, 2015). Useful negative immunohistochemical markers are Cytokeratins, S100, CD31 and Myogenin (Bohman et al., 2014). AFH are most often found in the dermis or the subcutaneous tissue of the extremities of children and young adults. But it has a wide age range (infants – adults in the 9th decade) and a part from other somatic localizations such as trunk, head and neck non-somatic locations have also been reported such as lung, mediastinum, retroperitoneum, vulva, omentum, bone and ovary (Chen et al., 2011; Shi et al., 2015; Tataroglu, Culhaci, & Cecen, 2015; Thway & Fisher, 2015; Thway, Stefanaki, Papadakis, & Fisher, 2013).

Differential diagnosis for the AFH are tumors or lesions such as inflammatory myofibroblastic tumor, follicular dendritic cell sarcoma, poorly differentiated carcinoma, meningioma, lymph node metastasis, hematoma, granulomatous inflammation, myoepithelioma, schwannoma, primary pulmonary myxoid sarcomas, Ewing sarcoma, rhabdomyosarcoma, malignant rhabdoid tumor or aneurysmal fibrous histiocytoma (Chen et al., 2011; Kao et al., 2014; Shi et al., 2015; Thway & Fisher, 2015).

Recent case reports and studies of the metastatic potential of these tumors have raised the question of and the necessity for a molecular or immunohistochemical marker or specific histological criteria that could correlate with the worse outcome for this particular group of patients. According to those studies metastasis was found in regional lymph nodes, bone and lung (Martinez, Moreno, Vinson, Dodd, & Brigman, 2016; Tay et al., 2016; Thway et al., 2013).

Also, in a recent study Cheah et al. reported on the results of ALK-expression of their series of eleven AFHs which showed that ALK expression in those tumors is common which had initially caused misdiagnosis as inflammatory myofibroblastic tumor which is one of the differential diagnostics of AFH (Cheah et al., 2018).

## **OBJECTIVE OF THE STUDY**

### **Primary Objective**

Primary objective is to present our series of AFH's with its clinical, histo-morphological and molecular characteristics of these tumors, in order to better understand their characteristics and to identify the best therapeutic approach.

### **Secondary Objective**

Secondary objective is to reproduce the results of ALK expression from the study of Cheah et al. on our series of 9 AFH's cases.

**STUDY DESIGN**

This is single institution cases series review of histological and clinical data

**POPULATION****Inclusion criteria**

- 1) Male and female patients treated at Rizzoli Institute from 01 January 2006 to 31 December 2017
- 2) Diagnosis of Angiomatoid Fibrous Histiocytoma
- 3) Histological slides/formalin-fixed paraffin-embedded tissue tumor (FFPE) blocks from archive available to perform the histology analysis
- 4) Written informed consent prior to any study-specific analysis and/or data collection

**Exclusion criteria**

- 1) Patients with histological diagnosis different from Angiomatoid Fibrous Histiocytoma

**MATERIAL AND METHODS**

We will retrieve from the archives of the Rizzoli Institute all the cases with a histological diagnosis of Angiomatoid Fibrous Histiocytoma. By reviewing our database, we expect to find approximately nine cases (actually all adults). We will review all the medical records, radiological imaging, and histological slides of all of these cases. In all cases with enough available material, immunohistochemistry will be performed on FFPE material. EWS-CREB1 and EWS-ATF1 mutation and ALK expression will be analyzed with RT-PCR and/or FISH analysis.

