**DATA COLLECTION**

Clinical data will be retrieved by patient charts.

A protocol-specific CRF reporting the results of the review will be provided.

A CRF is required and should be completed for each included subject.

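### Does the ALK result need a rule on whether the recorded or the reviewed AFH diagnosis defines the series?

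*Protocol*

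**What the plan says.** The Material and Methods section of the Protocol starts from the archive: "We will retrieve from the archives of the Rizzoli Institute all the cases with a histological diagnosis of Angiomatoid Fibrous Histiocytoma". About nine cases are expected from the institute's database. The next step is "We will review all the medical records, radiological imaging, and histological slides of all of these cases", followed by immunohistochemistry where tissue allows, and by RT-PCR and/or FISH for the fusions and ALK.

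The inclusion criterion on diagnosis is "Diagnosis of Angiomatoid Fibrous Histiocytoma". The only exclusion is "Patients with histological diagnosis different from Angiomatoid Fibrous Histiocytoma". Neither says whether the diagnosis meant is the one on file or the one reached on review.

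Under Secondary Objective, "Secondary objective is to reproduce the results of ALK expression" refers to another group's series of eleven AFH and is to be done in the institute's own nine cases. The Background reports of that series that "ALK expression in those tumors is common which had initially caused misdiagnosis as inflammatory myofibroblastic tumor". It also says that "molecular techniques such as FISH and PCR are recommended to make the diagnosis of an AFH".

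The Statistics section specifies descriptive statistics only. On recording, the Data Collection section says: "A protocol-specific CRF reporting the results of the review will be provided".

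**The concern.** Two things look loose.

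The first is how cases enter. A tumour still filed under another diagnosis is never retrieved. The Background names one route by which this could depend on ALK: ALK-positive AFH mistaken for inflammatory myofibroblastic tumour. If that had happened at this institute, the retrieved cases would hold too few ALK-positive tumours, and the comparison with the earlier series would be between differently composed groups.

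The second is how cases leave. Slide review and fusion assays can cast doubt on the diagnosis that brought a case in. The exclusion criterion could be read as removing such a case, and the retrieval sentence as keeping it. If the decision were taken after ALK had been read, the denominator could depend on the result being reported. With about nine cases, each one is visible in the percentage.

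**Working it through.** **1. What the text supports about the denominator.** These places bear on it.

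- Material and Methods retrieves by an existing histological diagnosis, and its expected count of about nine is a database count. The Secondary Objective uses the same nine. Both describe cases as filed.
- Inclusion criterion 4 requires consent before any study-specific analysis or data collection. The Enrollment Procedure includes patients already judged eligible, once they have consented. Eligibility is therefore judged before the study's slide review and assays, so on the diagnosis on file.
- The Background says that some AFH show no rearrangement by FISH, and that other tumours carry the same fusions. A negative or positive assay alone would therefore not settle whether a case is AFH, despite the recommendation of molecular techniques.
- The Background calls ALK expression common in AFH. A positive ALK result is thus no stated ground for dropping a case.

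The recorded diagnosis is the natural reading. What is left unstated is only how to present a case that the review reclassifies after inclusion.

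**2. Size of one reclassification.** The plan has no figure of its own to reproduce, since nine is a count and not a calculated sample size. The documents give no ALK-positive count, so assume x = 6 of n = 9.

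- All recorded cases: 6/9 = 66.7%.
- One ALK-positive case removed: (6 − 1)/(9 − 1) = 5/8 = 62.5%, a shift of −4.2 points.
- One ALK-negative case removed: 6/(9 − 1) = 6/8 = 75.0%, a shift of +8.3 points.

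The last two results belong to two different cases. A single decision moves the share by 4.2 or by 8.3 points, not by the 12.5 points between them.

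Other assumed counts give similar shifts. From 5/9 = 55.6%, one removal gives 4/8 = 50.0% or 5/8 = 62.5%. From 7/9 = 77.8%, it gives 6/8 = 75.0% or 7/8 = 87.5%.

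**3. Size of selection at entry.** Let p be the true ALK-positive share, and r the chance that an ALK-positive AFH is recognised as AFH relative to an ALK-negative one. Then

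observed share = p·r / (p·r + 1 − p).

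Neither input is in the documents. With p = 70% assumed:

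| r | Observed share |
|---|---|
| 0.5 | 0.35/0.65 = 53.8% |
| 0.8 | 0.56/0.86 = 65.1% |
| 1 | 70.0% |
| 1.25 | 0.875/1.175 = 74.5% |
| 2 | 1.4/1.7 = 82.4% |

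The shift can go either way, and its size follows wholly from the assumed r. Capping misfiling at 30% in either group gives 62% to 77% at p = 70%, but that cap has no source in the documents.

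**4. Against sampling error.** The exact (Clopper-Pearson) 95% interval for 6/9 is 29.9% to 92.5%, a half-width of (92.5 − 29.9)/2 = 31.3 points. For 5/9 it is 21.2% to 86.3%, and for 7/9 it is 40.0% to 97.2%. Every shift in steps 2 and 3 is smaller than that half-width.

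**The case for a change.** The best argument for a change is that who belongs to the series is an eligibility question, and so belongs in the protocol rather than in an analysis plan. By the protocol's own account, ALK has swayed this diagnosis before. Deciding a disputed case before ALK is read costs one sentence, and the order cannot be restored afterwards. Wide sampling error does not excuse an undefined denominator.

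Part of this stands. There is no explicit rule for a case reclassified on review, and writing one would do no harm.

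The rest is weaker. Nothing in the documents suggests that membership would be decided on ALK, that any AFH was misfiled at this institute, or that the review is meant to re-decide diagnoses; the Primary Objective is to describe the series. The case report form is not shown, and it is said to carry the results of the review, so the reviewed diagnosis may already be a field on it. In about nine cases reported descriptively, a reclassified tumour can be listed beside the others with its ALK result, and readers can form either fraction themselves.

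**Conclusion.** No change to the plan follows. The restriction to tumours recognised as AFH at this institute is what a single-institution case series means. The protocol declares that design and does not claim to estimate ALK expression in all AFH. The question of recorded or reviewed diagnosis is a gap in detail: the search, the count of nine and the order of consent before analysis point to the recorded diagnosis, and the investigators can be expected to handle a reclassified case openly.

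On an assumed 6 of 9, one such case moves the share by 4.2 or 8.3 points, against an exact interval of 29.9% to 92.5%. Selection at entry could shift the share either way; at an assumed true share of 70% and relative recognition between 0.5 and 2, the observed share runs from 53.8% to 82.4%. The data cannot reveal such an effect, and no test or threshold depends on it.

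The conclusion rests on the analysis staying descriptive, and on the ALK result being reported for this series and not as a rate for AFH at large.

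### The assay clause for ALK expression, the only secondary endpoint, allows FISH alone, which shows gene rearrangement and not expression

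*Protocol*

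**What the plan says.** The Secondary Objective section lists one aim: "Secondary objective is to reproduce the results of ALK expression" of a cited study, in the site's own nine cases. The Background gives the finding to be reproduced, referring to "their series of eleven AFHs which showed that ALK expression in those tumors is common".

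Material and Methods covers the laboratory work in two sentences. The first is general: "In all cases with enough available material, immunohistochemistry will be performed on FFPE material". It names no marker. The second assigns assays: "EWS-CREB1 and EWS-ATF1 mutation and ALK expression will be analyzed with RT-PCR and/or FISH analysis". Two fusion targets and one expression target thus share one list of techniques. No other part of the protocol ties ALK expression to an assay.

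The Background describes FISH as a test for rearrangement. It notes that "There is a certain number of AFH which are negative for all rearrangement with FISH", suggests "cryptic rearrangements of these genes undetectable by FISH" as one explanation, and adds that the genetic material may be "undetectable to the commercial break-apart probes".

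**The concern.** The endpoint is expression, but one of the listed techniques does not measure expression. FISH with break-apart probes shows whether a gene is structurally rearranged. RT-PCR can measure a transcript and is not at fault. The difficulty is that the clause lets FISH stand alone and does not ask for the same technique in every case.

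Two things follow if the text is applied as written. First, a case may be complete under the protocol and have no ALK expression result. Second, transcript results from some cases and rearrangement results from others may be tabulated together as ALK expression. A FISH result without rearrangement does not show that the tumor lacks ALK expression, yet nothing in the wording prevents it from being reported that way.

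The finding to be reproduced is that "ALK expression in those tumors is common". That is a statement about how often the tumor expresses ALK, so only cases with an expression result can be set against it.

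**Working it through.** The protocol gives no sample size, power or error-rate calculation for this endpoint, so there is no planned figure to reproduce. The check compares the endpoint with the assay and then asks how much a single case matters.

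**Inputs from the protocol**

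- Endpoint: ALK expression (Secondary Objective).
- Finding to be reproduced: expression is common in 11 cases (Background).
- Assays assigned: RT-PCR, FISH, or both (Material and Methods).
- Expected cases: about 9 (Secondary Objective; Material and Methods).
- Analysis: descriptive only (Statistics).

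**Step 1: what each permitted route yields for ALK**

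| Route | Result obtained | Expression result? |
|---|---|---|
| RT-PCR alone | transcript | yes |
| FISH alone | rearrangement status | no |
| Both | transcript and rearrangement status | yes |

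One route of three yields no expression result. This counts what the wording allows. It is neither a probability nor an estimate of affected cases.

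**Step 2: whether the Background supports this reading of FISH**

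Its remarks on FISH concern the diagnostic translocations and not ALK, but the kind of result is the same: a rearrangement is seen or it is not. The Background also discusses the pairing of RT-PCR with FISH as a way of detecting fusions. That pairing suits the two fusion targets in the Material and Methods sentence. It does not automatically suit the third.

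**Step 3: whether immunohistochemistry fills the gap**

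An ALK stain would give an expression result whichever molecular route was taken. The immunohistochemistry sentence names no marker, so an ALK stain is neither promised nor excluded. The next sentence then places ALK expression explicitly under RT-PCR and/or FISH. An expression result is therefore missing when both conditions hold: FISH is the only molecular assay for ALK, and no ALK stain is done.

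**Step 4: sensitivity to single cases**

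Let m be the number of cases meeting both conditions. The protocol does not give m, so its full range is 0 to 9. This assumes that all nine expected cases are included and have enough tissue.

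- Cases with an expression result: 9 − m. This runs from 9 (m = 0) through 8 (m = 1) and 6 (m = 3) to 0 (m = 9).
- If one case that does express ALK were recorded as negative on FISH, the observed proportion would fall by 1/9 = 0.111, or about 11 percentage points.

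The second figure shows how far one case can move a nine-case proportion. It does not say that any case will be misrecorded.

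**The case against.** The strongest reply is that the sentence is compressed and not wrong: three targets and two techniques are listed together, and an experienced pathology unit would apply to each target the technique that suits it. The authors clearly know that the two assays differ, since the Background sets out what each can and cannot show. On this view the text permits a mismatch but does not prescribe one. That is true, and the intended meaning may well be the sensible one. The sentence does not say so, however, and it is the only text that fixes the assay.

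A second reply is that the planned immunohistochemistry may include ALK, and that stain panels are often set outside the protocol. This also stands as a possibility, and it is why no loss of cases is asserted. It does not remove the problem, because the protocol assigns ALK expression elsewhere.

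Third, the aim is secondary and descriptive, in about nine archival cases, with no hypothesis test. That limits the severity. It does not make a FISH result an expression result.

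Finally, the protocol does not state which assay the cited series used, so the document cannot settle which expression assay would be a like-for-like reproduction. This is accepted: the document supports naming one expression assay, and the choice is the sponsor's. It can also be said that nothing in the protocol counts untested cases as negative. That is correct, and the conclusion does not depend on it.

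**Conclusion.** The point holds as a should-fix. The stated method does not fully fit the stated endpoint: one of three permitted routes gives no ALK expression result, and the wording allows different kinds of result to appear under one label. This is more than missing detail of the sort an SAP would supply, because the protocol does assign the assay and assigns one that can miss the endpoint.

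The conclusion rests on the literal wording and on FISH being a test of rearrangement, as the Background uses it. Confidence in that is high. Whether any case would actually lack an expression result depends on laboratory choices the protocol does not record, so no number of affected cases is claimed. RT-PCR, and the use of FISH for the two fusions, are not criticized.

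**What to change.** Split the assay sentence in Material and Methods.

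1. Keep RT-PCR and/or FISH for the EWS-CREB1 and EWS-ATF1 fusions only.
2. State that ALK expression will be measured by one named expression assay, the same in every case with enough tissue. The candidates already within the plan are ALK immunohistochemistry and RT-PCR. The sponsor should consult the cited series and choose the assay that matches it.
3. State that any ALK FISH result is reported separately as rearrangement status. As a safeguard, list a case without the expression assay as not assessed.

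The cost is a short change of wording and possibly one further stain or assay on limited archival tissue. The change should come before blocks are cut, because tissue used on another assay may not leave enough for the one the objective needs.

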**STATISTICS**

To the case series will be applied a descriptive statistic.

**ENROLLMENT PROCEDURE**

Patients considered eligible will be included in the study, after providing a written informed consent.

Due to the incidence of mortality of the disease under investigation, it would be possible that some eligible subjects will be deceased.

**DATA COLLECTION**

Clinical data will be retrieved by patient charts.

A protocol-specific CRF reporting the results of the review will be provided.

A CRF is required and should be completed for each included subject.

## **ETHICS AND QUALITY ASSURANCE**

The clinical trial protocol and its documents will be sent before initiating the study to the competent Authorities and Ethics Committees of each participating country for its approval.

The responsible investigator will ensure that this study is conducted in agreement with either the most updated Declaration of Helsinki and all the international and local laws that apply to clinical trials and to patient protection.

The protocol has been written, and the study will be conducted according to the principles of the ICH Harmonized Tripartite Guideline for Good Clinical Practice (ref: <http://www.emea.eu.int/pdfs/human/ich/013595en.pdf>).

